All of the statistical analyses, including ensuring the completeness and integrity of the data is being carried out by the Yale Center for Analytical Studies (YCAS) in conjunction with the personnel overseeing CTMS. YCAS is a relatively new center for collaborative science. Developed in partnership with the Yale Center for Clinical Investigation and the Yale School of Public Health (YSPH), YCAS brings together existing academic strengths in biostatistics, epidemiology, health economics and health services research at Yale. Their collaborative teams provide expertise in the design, conduct and analysis of health and healthcare studies, methodological development and education and training to Yale and the extended research community. YCAS operates in a vital and expanding YSPH community of scholars engaged in research that enhances the quality of the analytical and computational tools needed to effectively use the data being generated by rapidly advancing technology. Hence, it serves as a nexus for clinical investigators and analytical scientists with common interests to nurture the development and application of new approaches to design and data analysis.

Focus Groups: Data will be analyzed using the principles of grounded theory, using the constant comparative method for systematic inductive analysis. The transcripts from focus groups will be reviewed by members of the research team jointly who will perform data coding. We will develop the codes in a step-wise fashion, beginning with the creation of an initial code structure from the first two transcripts that are independently reviewed by each team member. All focus groups will be analyzed before initiating subsequent focus groups and new concepts will be used as probes in the subsequent interviews. To enhance inter-rater reliability, focus group transcripts will be independently reviewed and coded by each researcher and coding will be compared for agreement. Manual coding will then be electronically applied to the textual data using Dedoose a software program designed to facilitate the analysis of qualitative data. Data collected will be used to inform the development of the multiplayer videogame, *InvestiDate*.

Data Analyses General Considerations: Statistical procedures and models for analyzing data have been selected according to the research hypotheses being investigated and the types of data available. In general, we will use two-tailed tests and p-values smaller than 0.05 will be considered to indicate statistical significance. When necessary, however, we will use appropriate adjustment of the level of significance (alpha) to account for multiple statistical tests. All statistical analyses will be conducted on an intention-to-treat sample using either SPSS/SAS statistical packages. Baseline characteristics will be analyzed using descriptive statistics. We will use baseline, one-month, and four-month data to estimate effect sizes for the primary outcome. Given the limited sample size (n=80), we anticipate that the power of this study to identify small but significant effect sizes will be low. A strength of this design is that it provides a number of perspectives from which to view treatment effects, including a treatment condition, a control condition, and a follow-up period. The results will inform the sample size calculation for a subsequent full-scale randomized trial.

We will evaluate the preliminary efficacy of *InvestiDate* at increasing HIV/STI testing and partner HIV/STI testing. We will test the hypothesis that individuals who play *InvestiDate* will report more

HIV/STI testing and partner testing in comparison to the control condition. We will conduct a longitudinal analysis using a hierarchical linear mixed models approach to compare participants in the intervention group to participants in the control group on reported participant and partner HIV/STI testing from baseline across all follow-up assessments (i.e., baseline, one month and four months). Hierarchical modeling will allow us to account for the fact that the data are nested as the participants will play the game in groups. An advantage of mixed models is that participants with missing data need not be excluded as all available data are used in estimating parameters. We will also use logistic regression models to determine if any relevant baseline variables are associated with improvement in reported HIV/STI testing or partner testing (constructed as a binary outcome (Yes/No)). We plan to evaluate the prognostic significance of a small set of predictor variables (e.g., intentions, attitudes, self-efficacy, social norms, and knowledge) and use them as covariates in the primary analysis. All of these analyses will be exploratory given the study sample size.

SECTION II: RESEARCH INVOLVING DRUGS, BIOLOGICS, RADIOTRACERS, PLACEBOS AND DEVICES
--

- |                    |   |
|--------------------|---|
| A. RADIOTRACERS    |  N/A |
| B. DRUGS/BIOLOGICS |  N/A |
| C. DEVICES         |  N/A |

SECTION III: RECRUITMENT/CONSENT AND ASSENT PROCEDURES
---

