The card game prototype *One Night Stan* will be adapted as a multiplayer videogame called *InvestiDate* and will focus on a slightly younger age group. To do this we use formative research, pilot data, and focus group input to create an updated Game Playbook, or intervention manual that will be used to guide the development and design of the game.

**Phase 2: Pilot test *InvestiDate* compared with a control condition:** Participants will be randomly assigned to play either *InvestiDate* (n=40), or the non-health related attention and time control condition multiplayer videogame (n=40). Participants will be assigned to either the intervention or the control condition using a stratified randomization procedure. Age for the participant and partner testing in the last 30 days will be included in the randomization algorithm. Participants will be randomized by group so that the same group of participants will always play together.

**Assessments:** We will assess a range of pre-intervention participant characteristics (demographic), process measures, and outcomes (see below in Table 1). All assessments are standardized validated instruments that will be collected in person, using a web-based clinical trial management system we have used with our other studies. Assessments will be collected online using Yale-secured Qualtrics survey collection software. Baseline assessments are designed to ensure that all participants meet eligibility criteria and that important predictor variables are assessed. We will conduct post-intervention assessments immediately after gameplay sessions are completed (one month) with follow-up assessments at four months following enrollment to allow an adequate time for accumulation of outcome events.

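### The exploratory models for predictors of improved testing would be better fitted by Firth-penalised than by plain logistic regression with 80 girls; a minor, cheap improvement

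*Combined protocol and SAP*

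**What the plan says.** The analysis text is in Section I under Data Analyses General Considerations. After the main longitudinal mixed model it adds: "We will also use logistic regression models to determine if any relevant baseline variables are associated with improvement" in reported own or partner testing, an outcome "constructed as a binary outcome (Yes/No"). It continues: "We plan to evaluate the prognostic significance of a small set of predictor variables (e.g., intentions, attitudes, self-efficacy, social norms, and knowledge"), and says these variables will then serve as covariates in the main model. The paragraph closes by calling all of these analyses exploratory because of the sample size.

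The sample is 80 girls, 40 per arm, and the section concedes low power: "Given the limited sample size (n=80), we anticipate that the power of this study to identify small but significant effect sizes will be low". The general testing rule is that "we will use two-tailed tests and p-values smaller than 0.05 will be considered to indicate statistical significance", with adjustment for multiplicity when needed. SPSS and SAS are the named packages.

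The documents do not state the expected proportion of girls who improve, a cap on predictors, whether scales enter one at a time or together, which Table 1 instrument stands for each construct, any penalised fit, or a rule for choosing covariates.

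**The concern.** Unqualified logistic regression normally means maximum likelihood. With few events relative to the number of predictors, maximum likelihood pushes non-zero log odds ratios away from zero and makes them unstable. Eighty girls is a small base for several correlated psychosocial scales and an outcome that may be uncommon. If the scales go in together, a real predictor of testing would tend to look stronger than it is. The plan leaves open both the form of entry and the way covariates are chosen, so a reader cannot tell how exposed the results are. A standard alternative estimator removes most of the bias at almost no cost.

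**Working it through.** The plan gives no event count, event rate or events-per-predictor figure, so there is nothing of its own to reproduce.

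**Inputs from the documents**
- n = 80, with 40 per arm (Data Analyses General Considerations; Phase 2 description).
- Five constructs given as examples: intentions, attitudes, self-efficacy, social norms, knowledge.
- Matching Table 1 instruments: Intentions (1), MCAS (1), SRBBS and CUSES (2), Subjective Norms (1), HIV-KQ and STD-KQ (2). Total 1 + 1 + 2 + 1 + 2 = 7.

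**Assumptions, not in the documents**
- 8 to 40 girls improve (10% to 50%).
- One true predictor has odds ratio 1.5 per SD, so its log odds ratio is ln 1.5 = 0.405. The other predictors are null.
- Scales are standardised with pairwise correlation 0.3. There is no clustering.

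**Step 1. Events per predictor.** Formula: min(events, non-events) / number of predictors entered together. The smaller class cannot exceed 80/2 = 40.

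| Events | One scale per model | Five together | Seven together |
|---|---|---|---|
| 8 (10%) | 8 | 1.6 | 1.1 |
| 16 (20%) | 16 | 3.2 | 2.3 |
| 24 (30%) | 24 | 4.8 | 3.4 |
| 40 (50%, maximum) | 40 | 8.0 | 5.7 |

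If 15% were lost (assumed), 68 girls remain and the maximum for five predictors is 34/5 = 6.8.

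**Step 2. Bias by event rate.** 2,000 simulated data sets per setting, correlation 0.3. Relative bias = (mean estimated log odds ratio - 0.405) / 0.405. Ordinary fits that failed through separation or had fewer than two events (0.9% of runs with five predictors at 8 events) are excluded.

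| Events | One scale, ML | Five together, ML | Five together, Firth |
|---|---|---|---|
| 8 | +4% | +22% | -1% |
| 16 | +6% | +14% | 0% |
| 24 | +5% | +10% | -1% |
| 40 | +4% | +13% | +2% |

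**Step 3. Range over 8 to 40 events, adding arm to the single-scale model and including seven predictors**

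| Model | ML overstatement of log odds ratio | True 1.5 becomes | RMSE reduction with Firth |
|---|---|---|---|
| One scale plus arm | 5-9% | 1.53-1.56 | 6-11% |
| Five together | 8-24% | 1.55-1.65 | 11-27% |
| Seven together | 15-30% | 1.59-1.69 | 14-32% |

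The third column is exp(0.405 x (1 + overstatement)); for example exp(0.405 x 1.24) = 1.65. Firth stayed within about 4% throughout.

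**Step 4. Simulation error.** The largest standard error of an estimate in the joint fits was about 0.57. With 2,000 runs the error of the mean is 0.57/√2000 = 0.013, or 0.013/0.405 = 3% of the true value. Single cells can therefore move by several points. A separate run of 1,500 data sets put Firth with seven predictors at -6% and +6% for 8 and 12 events.

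**Step 5. If p < 0.05 were used to pick covariates.** With five scales together, the average odds ratio among significant results for the true predictor (1.5) was 3.8 at 8 events and 2.2 at 40. At least one of the four null scales was significant in 15-18% of runs.

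**The case against.** The strongest reply is that most of the harm depends on choices the plan has not made.

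- **Joint entry is not stated.** The text speaks of models in the plural and of any relevant variable. One-at-a-time fitting is equally consistent with it, and the bias is then small. This stands, and it makes the larger figures conditional.
- **Five or seven predictors is an inference.** The list is a small set of examples, and nothing commits the team to every instrument in Table 1. This also stands; the seven-predictor figures are an upper reading.
- **A reader might infer that events are too few at every event rate.** That needs joint entry and a threshold of 10 events per predictor, which the documents never mention. At 5 per predictor, five scales pass from 25 events (25/80 = 31%), and single-scale models reach 10 from 10/80 = 12.5%.
- **A reader might infer that significant predictors will be picked for the primary model.** No selection rule is written, and the sentence can mean that the whole named set is used. The primary analysis is a linear mixed model, so the size of a logistic odds ratio does not enter it.
- **The bias is small beside sampling error.** In joint fits it was 0.04-0.13 on the log scale against standard errors of 0.29-0.57, about one-seventh to one-quarter of a standard error. It also concerns truly associated predictors; null ones are not inflated in the same proportional way.
- **The limits are disclosed.** The analyses are labelled exploratory and low power is admitted.

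What survives is narrower. The label limits what may be claimed but does not correct the estimator, and low power is not the same as upward bias. Even in single-scale models Firth had the lower RMSE.

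**Conclusion.** The point holds as a minor improvement. If the named constructs are entered together, maximum likelihood would overstate the log odds ratio of a real predictor by about 8-24% with five scales and 15-30% with seven. With one scale plus arm per model the figure is about 5-9%. Firth fitting brings this to within about 4% and lowers RMSE in each case. These sizes rest on the assumed odds ratio, correlation and event counts, and on ignoring the play groups.

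The documents do not support saying that events are too few at any event rate. Nor do they support saying that these odds ratios will be carried into the full trial: the plan says only that results will inform its sample-size calculation, and does not say that the prognostic odds ratios are an input. Selection on p-values would be a larger problem than the estimator, but it is a possibility left open and not something the plan states.

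**What to change.** In Data Analyses General Considerations, where the logistic models are described, state that:

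1. these exploratory models are fitted by Firth-penalised logistic regression with profile-likelihood confidence intervals;
2. one instrument per construct is chosen beforehand, so that knowledge and self-efficacy contribute one scale each;
3. each predictor is reported adjusted for arm, followed by one joint penalised model of the chosen scales;
4. p-values from these models are not used to choose covariates for the primary analysis.

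The cost is a few sentences and the use of SAS, one of the two packages already named, for this step. No extra participants or data are needed. The statistical price is slight shrinkage of estimates toward the null. Firth fitting does not deal with clustering by play group, which is a separate matter.

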## SECTION I: RESEARCH PLAN

1. **Statement of Purpose:** State the scientific aim(s) of the study, or the hypotheses to be tested.

The purpose of this study is to develop and evaluate an innovative behavioral HIV prevention videogame intervention to bolster motivation and provide skill-building opportunities to improve Black adolescent girls' ability to negotiate around risk including advocating for partner HIV/STI testing, increasing their knowledge and awareness of HIV/STIs, and for reducing sexual risk-taking behaviors (1.e. non-condom use). As a multiplayer videogame, the intervention will be developed and delivered as a social, multiplayer videogame, a compelling context for Black adolescent girls who constantly interact and seek counsel from their peers.

To this end, our Specific Aims, focusing on Black adolescent girls aged 14-18 years, are to:

1. Translate our culturally and socially-tailored card game *One Night Stan* to a multiplayer videogame using game design and content experts and focus group input from 30 Black adolescent girls.
  2. Conduct a pilot randomized controlled trial comparing the multiplayer videogame *InvestiDate* intervention vs. an attention/control non-health-related multiplayer videogame with 80 participants collecting assessment data at baseline, one, and four months to:
    - a. Determine the intervention's acceptability and feasibility by collecting quantitative and qualitative data on Black adolescent girls' satisfaction and gameplay experience of the intervention.
    - b. Determine the preliminary impact of the intervention on knowledge (information), intentions/attitudes (motivation), social norms, and behavioral skills as related to: i) HIV/STI testing and partner testing and ii) condom use, and iii) sexual risk behavior reduction, such as alcohol and drug use.
2. **Probable Duration of Project:** State the expected duration of the project, including all follow-up and data analysis activities.
 

2 years
  3. **Background:** Describe the background information that led to the plan for this project. Provide references to support the expectation of obtaining useful scientific data.

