**Table 1: Assessments**

Assessment	Base-line	Month 1	Month 4
Participant Demographics (i.e. gender, age, education)	X		
HIV/STI Testing Rates and Partner HIV/STI Testing Rates	X	X	X
Sexual Risk Behaviors—Self-reported measures of sexual intercourse with/without condoms 	X	X	X
Vulnerability to Risky Sexual Behaviors 	X	X	X
Risk Behaviors Associated with HIV/STIs - Youth Risk Behavior Survey 	X	X	X
HIV Knowledge (HIV-KQ)  (45 item true/false questionnaire)	X	X	X
STI Knowledge (STD-KQ)  (27-item true/false questionnaire)	X	X	X
Subjective Norms 	X	X	X
Intentions 	X	X	X
Attitudes—Multi-dimensional Condom Attitudes Scale (MCAS) 	X	X	X
Self-efficacy in sexual risk behaviors—Sexual Risk Behavior Beliefs and Self-efficacy (SRBBS) Scales 	X	X	X
Condom Self-Efficacy (CUSES)  (28-item Likert scale)	X	X	X
Sexual Communication 	X	X	X
*Satisfaction with game play/acceptability and feasibility (12-item Likert scale) 		X	

5. **Genetic Testing** N/A

6. **Subject Population:** Provide a detailed description of the types of human subjects who will be recruited into this study.

Adolescents ages 14-18 will be recruited into this study.

7. **Subject classification:** Check off all classifications of subjects that will be specifically recruited for enrollment in the research project. Will subjects who may require additional safeguards or other considerations be enrolled in the study? If so, identify the population of subjects requiring special safeguards and provide a justification for their involvement.

- |  |  |  |
|--|--|--|
|  Children   |  Healthy                |  Fetal material, placenta, or dead fetus |
|  Non-English Speaking  |  Prisoners                         |  Economically disadvantaged persons      |
|  Decisionally Impaired |  Employees                         |  Pregnant women and/or fetuses           |
|  Yale Students         |  Females of childbearing potential |  |

NOTE: Is this research proposal designed to enroll children who are wards of the state as potential subjects?

Yes  No

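### The primary-analysis covariates are left to an open-ended prognostic evaluation, and the two randomisation factors are not named among them; the cost is modest and the remedy is a short fixed baseline list

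*Combined protocol and SAP*

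**What the plan says.** The analysis text is in Section I, under Data Analyses General Considerations and the paragraph after it.

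- **Model.** A hierarchical linear mixed model compares the arms on reported own and partner HIV/STI testing at baseline, one month and four months, with play group as a level of nesting.
- **Predictor step.** Logistic regression will "determine if any relevant baseline variables are associated with improvement in reported HIV/STI testing or partner testing".
- **Covariates.** The next sentence plans to "evaluate the prognostic significance of a small set of predictor variables". It describes them as "a small set of predictor variables (e.g., intentions, attitudes, self-efficacy, social norms, and knowledge) and use them as covariates in the primary analysis".
- **Status.** All of these analyses are called exploratory. The general considerations set a two-sided 0.05 level, expect low power with n=80, and say that the results will inform the sample size of a full-scale trial.

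Elsewhere:

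- Item 1, Aim 2b, sets out to "Determine the preliminary impact of the intervention on knowledge (information), intentions/attitudes (motivation), social norms, and behavioral skills".
- Table 1 collects the scales for these constructs, and "HIV/STI Testing Rates and Partner HIV/STI Testing Rates", at baseline, month 1 and month 4.
- Item 4 (Phase 2) puts age and partner testing in the last 30 days into the randomisation algorithm, with allocation by play group. Its Assessments paragraph says that the baseline assessments capture the important predictors.

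The supplied analysis text names neither randomisation factor as a covariate. A portion of the document just ahead of that text was not available, so statements of absence cover only what was supplied.

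**The concern.** Two analysts could follow this text faithfully and fit different primary models. The list is introduced by examples, two of the five constructs have two instruments each, and no rule says how the prognostic evaluation decides what enters. The two variables with the clearest claim to a place in the model, because the allocation was built on them, are not mentioned.

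At stake are precision and stability. Leaving out a prognostic stratification factor makes the standard error too wide for the design. An unsettled choice of instrument lets the arm estimate move for reasons unrelated to the intervention. The estimate is meant to help size the next trial, so it is worth fixing what can be fixed.

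**Working it through.** **1. How open is the list?** The plan gives no figure to reproduce, so the constructs are matched to Table 1.

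| Construct | Instruments in Table 1 |
|---|---|
| Intentions | Intentions |
| Attitudes | MCAS |
| Social norms | Subjective Norms |
| Knowledge | HIV-KQ, STD-KQ |
| Self-efficacy | SRBBS, CUSES |

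If every construct must be represented, knowledge can be covered in 3 ways (either instrument or both) and self-efficacy in 3. That gives 3 x 3 x 1 x 1 x 1 = 9 covariate sets.

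**2. How far does that choice move the estimate?** The documents give no testing rates, group size or intracluster correlation (ICC), so the following are assumed:
- 80 girls in 16 play groups of five, groups stratified, with a random group effect.
- 15% with 30-day partner testing at baseline.
- Control rate about 20%: 0.15 x 45.5% + 0.85 x 15.5% = 20.0%.
- Scales correlated 0.4 (0.6 within the knowledge and self-efficacy pairs).
- Scales either not prognostic, or three worth 4 points per SD, or all worth 2 points per SD.
- No true effect; 1,500 simulated trials per scenario.

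The gap between the largest and smallest of the nine estimates had a median of 2.1-2.4 percentage points (90th percentile 4.6-5.3), against a standard error of 9-10. The median gap is therefore between 2.1/10 = 0.21 and 2.4/9 = 0.27 of a standard error. Using all seven instruments made the standard error 6-9% larger than the fixed list did.

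**3. What does omitting baseline partner testing cost in a month-4 model?** Let p = 0.15 be the share with the factor, r1 their month-4 rate (assumed 60%, 40% or 25%) and r0 = 10% the rate in the others. With balanced arms:

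SE ratio ≈ √[(W + B)/W], where W = p·r1(1−r1) + (1−p)·r0(1−r0) and B = p(1−p)(r1−r0)².

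| r1 | W | B | SE ratio |
|---|---|---|---|
| 60% | 0.15×0.24 + 0.85×0.09 = 0.1125 | 0.1275×0.25 = 0.0319 | 1.133 |
| 40% | 0.15×0.24 + 0.85×0.09 = 0.1125 | 0.1275×0.09 = 0.0115 | 1.050 |
| 25% | 0.15×0.1875 + 0.85×0.09 = 0.1046 | 0.1275×0.0225 = 0.0029 | 1.014 |

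Simulating individuals with exact balance gives 1.146, 1.059 and 1.018. These are a little higher because only 0.15 x 80 = 12 girls carry the factor and their outcomes are more variable.

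With play groups, a random group effect and an age effect of 8 points (3,000 trials per scenario), the ratios for omitting both factors were:
- ICC 0: 1.147, 1.059, 1.018.
- ICC 0.05: 1.123, 1.048, 1.016.
- Unstratified groups: standard error 1-13% larger.
- Individual allocation with groups formed within arm: 2-15% larger.

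Under stratified groups the true sampling SD rose by only 1-6%, so much of the penalty is a standard error that overstates the uncertainty. Power for a 20-point effect fell by 0-7 points (41.0% against 48.1% at worst). The ratio for baseline partner testing alone against both factors was 0.998-1.007, so age contributes under 1%.

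**4. From the month-4 model to the planned one.** The plan analyses testing "from baseline across all follow-up assessments (i.e., baseline, one month and four months"), so baseline partner testing is already in the model as a response. Two parametrisations bracket the consequence:
- A common baseline mean with unstructured covariance, fitted without a group effect, gave the same month-4 estimate as regression on arm and baseline (difference below 1e-15; SE ratio 0.991-0.993). Nothing is lost.
- Separate baseline means per arm, a random intercept and an arm-by-month-4 contrast gave a sampling SD 5-16% larger than the fixed list.

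The plan states neither.

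**5. Type I error.** In the step 3 simulations, rejection under no effect was 2.2-3.4% without the factors and 2.2-3.6% with them. Retaining scales at p<0.05 gave 1.9-3.1%. None exceeds the nominal 5%.

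**The case against.** The strongest reply is that the 2-15% figure comes from a model the plan does not propose. The longitudinal model contains baseline partner testing, age hardly matters, and under one ordinary parametrisation the loss is nil. This stands, and it limits the size of the point. It does not remove it: the parametrisation is unstated, the baseline response is not said to use the 30-day definition, and age does not enter at all.

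The plan also speaks of a small set and of using the variables, which can be read as including all of them. That narrows the choice but does not close it, because nine instrument sets still qualify. Their spread is small beside sampling error, as the reply would rightly add, and it is a maximum-minus-minimum range, not the gap between two likely choices.

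Three stronger readings are tempting and not supported:

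- **Follow-up scale values would be entered, adjusting away part of the effect.** The covariate sentence does not exclude this. But the Assessments paragraph ties predictors to the baseline visit, and the preceding sentence concerns baseline variables. Baseline values are the natural reading, and they are legitimate covariates even for scales that are also outcomes.
- **False positives would be inflated.** That would need an analyst to choose the set with sight of the arm effect. In an individual-level simulation, taking the most favourable of 32 sets gave 6.9-13.0%. The plan proposes nothing of the kind.
- **All five constructs are Aim 2b outcomes.** Four are named there. Self-efficacy fits only by inference, under behavioral skills.

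**Conclusion.** The point holds as a modest matter of precision and stability. The primary-analysis covariates are not fixed, and the supplied text does not name the two randomisation factors among them.

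The sizes rest on assumed rates, group size and ICC. The loss from omitting baseline partner testing runs from nil to the month-4 range, or somewhat different under other parametrisations, depending on how baseline is handled. Instrument choice adds about a quarter of a standard error or less at the median.

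The exploratory label and the admission of low power lower the stakes. Sampling error with 80 girls will dominate whatever is carried into the next trial's sample size. The change is still worth making: the text refers to a primary analysis, the better specification is concrete, and it is nearly free.

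**What to change.** In the primary analysis, replace the prognostic-evaluation step with a fixed list of baseline covariates:

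- age;
- partner testing in the last 30 days;
- the baseline value of the outcome, where it varies. Item 8 excludes girls tested for HIV in the past year, so their own recent HIV testing cannot vary at baseline; STI testing and partner testing can.

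Enter baseline once: either as a covariate with months 1 and 4 as responses, or as a response with a common baseline mean across arms and unstructured covariance. Where the outcome is partner testing on the 30-day definition, the randomisation factor and the baseline outcome are the same variable and should not appear twice. Keep the play-group effect.

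Keep the psychosocial scales for the separate exploratory predictor analysis, with each instrument named and only baseline values used.

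The cost is SAP wording and two or three degrees of freedom, against seven if every instrument behind the five constructs were entered. The variables are already collected at baseline or needed for randomisation.
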